**Table 6 Schedule of Assessments in Study E7080-G000-230 – Extension Phase**

Phase	Extension a		
Period	Treatment Period a		Follow-up Period
Visit	98	99	
Cycle	Cycle X +1 and beyond	Off-Tx Visit	
Day	1		
Procedures/Assessments			
Pregnancy test b	X	X	
Lansky play score/ Karnofsky PS c	X	X	
Physical examination d	X	X	
Vital signs e	X	X	
12-lead ECG f	As clinically indicated		
Echocardiogram g	As clinically indicated		
Clinical chemistry and hematology h	X	X	
Urine dipstick testing i	X	X	
Study treatment j	Arm A: Lenvatinib a		
Tumor assessments: CT/MRI k	After data cutoff, tumor assessments may be performed as clinically indicated as per the institutional guidelines, following the prevailing local standard of care.		
Brain CT/MRI l	After data cutoff, tumor assessments may be performed as clinically indicated as per the institutional guidelines, following the prevailing local standard of care.		
Height m	To be checked every 4 cycles	X	X
Tanner Stage n		X	X
Proximal Tibial growth plates x-ray o		X	
Survival p	X		X
Concomitant medications q	Throughout		X
AEs/SAEs r	Throughout		X

AE = adverse event, CT = computerized tomography, ICL = imaging core laboratory, MRI = magnetic resonance imaging, PD = disease progression, PS = performance status, SAE = serious adverse event.

a. Subjects benefiting from study treatment in the opinion of the investigator will continue treatment until PD, intolerable toxicity, subject request, subject noncompliance with safety or efficacy assessments, voluntary discontinuation by the subject at any time, or study termination by the sponsor, whichever occurs first.

**Table 6 Schedule of Assessments in Study E7080-G000-230 – Extension Phase**

Phase	Extension a	
Period	Treatment Period a	Follow-up Period
Visit	98	99
Cycle	Cycle X+1 and beyond	Off-Tx Visit
Day	1	

- b. A serum or urine pregnancy test will be performed on Day 1 of each cycle and at the Off-treatment Visit in women of childbearing potential.
- c. A Lansky play score or Karnofsky performance status score will be obtained at Day 1 of every cycle visit.
- d. A physical examination will be performed at Day 1 visit of each cycle, and at the Off-treatment Visit. A symptom-directed physical examination will be performed at any time as clinically indicated.
- e. Assessments will include vital signs (resting BP, HR, RR, and body temperature), and weight. Blood pressure that is consistently above the 95th percentile for sex, age, and height/length requires further evaluation. Refer to hypertension management guidelines in [Section 8.4.1.1.2](#).
- f. Single 12-lead ECG. Subjects must be in the recumbent position for a period of 5 minutes prior to the ECG.
- g. An echocardiogram is performed as clinically indicated.
- h. Clinical chemistry and hematology results must be reviewed within 48 hours after administering any study drug for all subsequent cycles. Scheduled assessments may be performed within 72 hours prior to the visit. If  $\geq$ Grade 3 hematologic or clinical chemistry toxicity, repeat laboratory test and AEs assessment at least every 3 days (until improvement to  $<$ Grade 3). TSH should be assessed for all subjects.
- i. Urine dipstick testing should be performed on Day 1 of every cycle, or more frequently as clinically indicated, and at the Off-treatment Visit. For subjects with a history of proteinuria  $\geq$ 2+, urine dipstick testing should be performed until the results have been 1+ or negative for 2 consecutive cycles. If a new event of proteinuria  $\geq$ 2+ occurs, refer to [Section 8.4.1.1.4](#) for further management guidelines. Urine glucose should be performed as part of the urine dipstick.
- j. Subjects randomized to Arm A will continue to receive lenvatinib only until progressive disease, unacceptable toxicity, or withdrawal of consent.
- k. After data cutoff, tumor assessments may be performed as clinically indicated as per the institutional guidelines, following the prevailing local standard of care. The scans will no longer be required to be sent to the ICL.
- l. Brain CT with contrast or MRI pre- and post- gadolinium contrast will be performed as per the institutional guidelines, following the prevailing local standard of care.
- m. Height will be assessed at the Baseline Visit, Day 1 of every 4 cycles during the Treatment Phase, at the Off-treatment Visit and every 3 months during the Post-treatment Follow-up.
- n. Tanner Stage will be assessed at the Baseline Visit, at the Off-treatment Visit, and annually thereafter during the Post-treatment Follow-up.
- o. Proximal tibial growth plates x-rays should be conducted at baseline and at the Off-treatment Visit. If the growth plates are closed at baseline then the subject does not need a reassessment at the Off-treatment Visit. Tibial growth plate x-rays will be optional for Germany.
- p. Survival data will be collected every 3 months until death as per the protocol. All anticancer therapies will be collected.
- q. Concomitant medications will be recorded throughout the study and for 30 days after last dose. All anticancer therapy will be recorded until time of death or termination of Survival Follow-up.
- r. AEs will be recorded from the date of signed informed consent, throughout the study, and for 30 days after last dose. SAEs irrespective of relationship to study treatment must be reported as soon as possible but not later than 24 hours.

#### 8.5.2.2 Description of Procedures/Assessments Schedule

Refer to [Table 5](#) for schedule and description of procedures in the Randomization Phase and [Table 6](#) for the Extension Phase.

#### 8.5.3 Appropriateness of Measurements

All clinical assessments are standard measurements commonly used in studies of relapsed or refractory solid tumors.

The safety assessments to be performed in this study, including hematology analyses, blood chemistry tests, urinalysis, radiologic studies, and assessment of AEs, are standard evaluations to ensure subject safety. The use of RECIST 1.1 for tumor assessments of solid tumors is widely accepted (see [Appendix 1](#)) ([Eisenhauer, et al., 2009](#)).

### 8.5.4 Reporting of Serious Adverse Events, Pregnancy, and Events Associated with Special Situations

#### 8.5.4.1 Reporting of Serious Adverse Events

**All SERIOUS ADVERSE EVENTS, regardless of their relationship to study treatment, must be reported on a completed SAE form by email or fax as soon as possible but no later than 24 hours from the date the investigator becomes aware of the event.**

Serious adverse events, regardless of causality assessment, must be collected for 30 days after the subject's last dose. All SAEs must be followed to resolution or, if resolution is unlikely, to stabilization. Any SAE judged by the investigator to be related to the study treatment or any protocol-required procedure should be reported to the sponsor regardless of the length of time that has passed since study completion.

The detailed contact information for reporting of SAEs is provided in the Investigator Study File.

**For urgent safety issues**, please ensure all appropriate medical care is administered to the subject and contact the appropriate study team member listed in the Investigator Study File.

It is very important that the SAE report form be filled out as completely as possible at the time of the initial report. This includes the investigator's assessment of causality.

Any relevant follow-up information received on SAEs should be forwarded within 24 hours of its receipt. If the relevant follow-up information changes the investigator's assessment of causality, this should also be noted on the follow-up SAE form.

Preliminary SAE reports should be followed as soon as possible by detailed descriptions including copies of hospital case reports, autopsy reports, and other documents requested by the sponsor.

The investigator must notify his/her IRB/IEC of the occurrence of the SAE in writing, if required by their institution. A copy of this communication must be forwarded to the sponsor and/or the designated CRO monitor to be filed in the sponsor's Trial Master File.

#### 8.5.4.2 Reporting of Pregnancy and Exposure to Study Drug Through Breastfeeding

Any pregnancy in a female subject in which the estimated date of conception is either before the last visit or within 30 days of last study treatment, or any exposure to study drug through breastfeeding during study treatment or within 30 days of last study treatment, must be reported.

If an adverse outcome of a pregnancy is suspected to be related to study drug exposure, this should be reported regardless of the length of time that has passed since the exposure to study treatment.

A congenital anomaly, death during perinatal period, a spontaneous abortion or an induced abortion done due to safety concerns for either mother or fetus are considered to be an SAE and should be reported in the same time frame and in the same format as all other SAEs (see Reporting of Serious Adverse Events [Section 8.5.4.1]).

Pregnancies or exposure to study drug through breastfeeding must be reported by fax or email as soon as possible but no later than 24 hours from the date the investigator becomes aware of the pregnancy. The contact information for the reporting of pregnancies and exposure to study drug through breastfeeding is provided in the Investigator Study File. The Pregnancy Report Form must be used for reporting. All pregnancies must be followed to outcome. The outcome of the pregnancy must be reported as soon as possible but no later than 24 hours from the date the investigator becomes aware of the outcome.

A subject who becomes pregnant must be withdrawn from the study.

#### 8.5.4.3 Reporting of Events Associated with Special Situations

##### 8.5.4.3.1 REPORTING OF ADVERSE EVENTS ASSOCIATED WITH STUDY DRUG OVERDOSE, MISUSE, ABUSE, OR MEDICATION ERROR

Adverse events associated with study drug overdose, misuse, abuse, and medication error refer to AEs associated with uses of the study drug outside of that specified by the protocol. Overdose, misuse, abuse, and medication error are defined as follows:

Overdose	Accidental or intentional use of the study drug in an amount higher than the protocol-defined dose
Misuse	Intentional and inappropriate use of study drug not in accordance with the protocol
Abuse	Sporadic or persistent intentional excessive use of study drug accompanied by harmful physical or psychological effects

**Medication error** Any unintentional event that causes or leads to inappropriate study drug use or subject harm while the study drug is in the control of site personnel or the subject.

All AEs associated with overdose, misuse, abuse, or medication error should be captured on the Adverse Event CRF and also reported using the procedures detailed in Reporting of Serious Adverse Events ([Section 8.5.4.1](#)) even if the AEs do not meet serious criteria. Abuse and Intentional Overdose, even if asymptomatic, are always to be captured as an AE. If the AE associated with an overdose, misuse, abuse, or medication error does not meet serious criteria, it must still be reported using the SAE form and in an expedited manner but should be noted as nonserious on the SAE form and the Adverse Event CRF.

#### 8.5.4.3.2 REPORTING OF ABNORMAL HEPATIC TESTS OF CLINICAL INTEREST

The following combination of abnormal laboratory tests\*, as determined by way of protocol-specified laboratory testing or unscheduled laboratory testing and whether nonserious or serious, should be entered on the Adverse Event CRF and reported using the procedures detailed in Reporting of Serious Adverse Events ([Section 8.5.4.1](#)). If the event does not meet serious criteria, the seriousness criteria on the SAE form should be indicated as “nonserious.”

- Elevated AST or ALT lab value that is greater than or equal to  $3\times$  the upper limit of normal  
AND
- Elevated total bilirubin lab value that is greater than or equal to  $2\times$  the upper limit of normal  
AND AT THE SAME TIME
- Alkaline phosphatase lab value that is less than  $2\times$  the upper limit of normal

\*Note: These criteria are based upon available regulatory guidance documents. The purpose of the criteria is to specify a threshold of abnormal hepatic tests that may require additional evaluation for an underlying etiology. In addition to reporting the abnormal hepatic laboratory tests on a SAE form, the site should also consult the medical monitor for guidance on assessment and follow-up. At a minimum, laboratory testing should be repeated at least once weekly until improvement or identification of a cause unrelated to study drug use that is unlikely to improve.

#### 8.5.4.4 Expedited Reporting

The sponsor must inform investigators and regulatory authorities of reportable events, in compliance with applicable regulatory requirements, on an expedited basis (ie, within specific time frames). For this reason, it is imperative that sites provide complete SAE information in the manner described above.

#### 8.5.4.5      **Breaking the Blind**

Not applicable

#### 8.5.4.6      **Regulatory Reporting of Adverse Events**

Adverse events will be reported by the sponsor or a third party acting on behalf of the sponsor to regulatory authorities in compliance with local and regional law and established guidance. The format of these reports will be dictated by the local and regional requirements.

All studies that are conducted within any European country will comply with European Good Clinical Practice Directive 2005/28/EC and Clinical Trial Directive 2001/20/EC. All SUSARs will be reported, as required, to the competent authorities of all involved European member states.

#### 8.5.5      **Completion/Discontinuation of Subjects**

A subject (or subject's parent or guardian) may elect to discontinue study drug at any time for safety, medical, or personal reasons. Subjects who choose to discontinue study drug prior to PD will be followed in the post-study treatment follow-up period and continue to undergo regularly scheduled disease assessment until documentation of PD or start of an alternative anticancer treatment. All subjects who discontinue study drug will be followed for OS and all post progression cancer treatments administered will be recorded. Subjects may at any time withdraw consent for further study participation. No further data will be collected on subjects once consent has been withdrawn. All subjects who discontinue the study are to complete the study's early discontinuation procedures indicated in the Schedule of Assessments ([Table 5](#) and [Table 6](#)).

The investigator will promptly explain to the subject (or subject's parent or guardian) involved that the study will be discontinued for that subject and provide appropriate medical treatment and other necessary measures for the subject. A subject who has ceased to return for visits will be followed up by mail, phone, or other means to gather information such as the reason for failure to return, the status of treatment compliance, the presence or absence of AEs, and clinical courses of signs and symptoms.

Subjects who discontinue early from the study will be discontinued for 1 of these primary reasons: AE(s), lost to follow-up, subject choice, progression of disease, withdrawal of consent, pregnancy, study terminated by sponsor, or administrative/other. In addition to the primary reason, the subject may indicate 1 or more secondary reason(s) for discontinuation. Study disposition information will be collected on the Subject Disposition CRF.

#### 8.5.6      **Abuse or Diversion of Study Drug**

Not applicable.

### **8.5.7 Confirmation of Medical Care by Another Physician**

The investigator will instruct subjects to inform site personnel when they are planning to receive medical care by another physician. At each visit, the investigator will ask the subject whether he/she has received medical care by another physician since the last visit or is planning to do so in the future. When the subject is going to receive medical care by another physician, the investigator, with the consent of the subject, will inform the other physician that the subject is participating in the clinical study.

## **8.6 Data Quality Assurance**

This study will be organized, performed, and reported in compliance with the protocol, SOPs, working practice documents, and applicable regulations and guidelines. Site audits will be made periodically by the sponsor's or the CRO's qualified compliance auditing team, which is an independent function from the study team responsible for conduct of the study.

### **8.6.1 Data Collection**

Data required by the protocol will be collected on the CRFs and entered into a validated data management system that is compliant with all regulatory requirements. As defined by ICH guidelines, the CRF is a printed, optical, or electronic document designed to record all of the protocol-required information to be reported to the sponsor on each study subject.

Data collection on the CRF must follow the instructions described in the CRF Completion Guidelines. The investigator has ultimate responsibility for the collection and reporting of all clinical data entered on the CRF. The investigator or designee must sign the completed CRF to attest to its accuracy, authenticity, and completeness.

Completed, original CRFs are the sole property of Eisai and should not be made available in any form to third parties without written permission from Eisai, except for authorized representatives of Eisai or appropriate regulatory authorities.

### **8.6.2 Clinical Data Management**

All software applications used in the collection of data will be properly validated following standard computer system validation that is compliant with all regulatory requirements. All data, both CRF and external data (eg, laboratory data), will be entered into a clinical system.

## **8.7 Statistical Methods**

All statistical analyses will be performed by the sponsor or designee after the study is completed, the database is locked and released, a snapshot of the database is obtained and released, and randomization codes have been released and applied. Statistical analyses will be performed using SAS software or other validated statistical software as required. Details of the statistical analyses will be included in a separate statistical analysis plan (SAP).

## 8.7.1 Statistical and Analytical Plans

The statistical analyses of study data are described in this section. Further details of the analytical plan will be provided in the SAP, which will be finalized before database lock.

### 8.7.1.1 Study Endpoints

#### 8.7.1.1.1 PRIMARY ENDPOINT

- Progression-free survival rate at 4 months (PFS-4m rate) by IIR is defined as the percentage of subjects who are alive and without PD at 4 months from the randomization date as determined by IIR of radiological imaging using RECIST 1.1. The PFS-4m rate is estimated on the full analysis set for this study using the K-M method.

#### 8.7.1.1.2 SECONDARY ENDPOINTS

- Progression-free survival rate at 1 year (PFS-1y rate) by IIR is defined as the percentage of subjects who are alive and without PD at 1 year from the randomization date as determined by IIR of radiological imaging using RECIST 1.1. The PFS-1y rate is estimated on the full analysis set for this study using the K-M method.
- Progression-free survival (PFS) by IIR is defined as the time from the date of randomization to the date of the first documentation of PD or death (whichever occurs first) as determined by IIR using RECIST 1.1.
- Overall survival (OS) is defined as the time from the date of randomization to the date of death from any cause. Subjects who are lost to follow-up and those who are alive at the date of data cutoff will be censored at the date the subject was last known alive, or date of data cutoff, whichever occurs first. Overall survival rate at 1 year will be estimated.
- Objective response rate (ORR) by IIR at 4 months is defined as the proportion of subjects who have best overall response of complete response (CR) or partial response (PR) as determined by IIR using RECIST 1.1 within the first 4 months.
- Safety will be assessed summarising the incidence of TEAEs and SAEs together with all other safety parameters.
- Assessment of population-based PK parameters of lenvatinib.
- Score changes from baseline for all PedsQL scales including Generic Core Scales and Cancer Module. Scores will be calculated for total generic score, total cancer score, each physical function subscale including physical health, psychosocial health, emotional function, social function, school/work function in the Generic Core Scales, and each subscales in the cancer module.
- Palatability and acceptability of the suspension formulation of lenvatinib in subjects receiving the suspension formulation in the study will be assessed using the Palatability Questionnaire (see [Appendix 5](#)).

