### *During Treatment Phase*

CT/MRI scans of, chest, abdomen, pelvis, and other known sites of disease plus any areas of newly suspected disease will be performed using the same methodology as at screening every 6 weeks  $\pm$ 1 week, following the start of treatment on Cycle 1 Day 1 during the chemotherapy treatment period until Week 18. Following completion of the chemotherapy treatment period (ie, after Week 18), the frequency of tumor assessments will be every 9 weeks  $\pm$ 1 week until Week 54  $\pm$ 1 week. Thereafter, they will be performed every 12 weeks  $\pm$ 2 weeks until documentation of PD. At any point, scans should be performed earlier than the scheduled time point, if clinically indicated.

An initial assessment of CR or PR according to RECIST 1.1 must be confirmed by IIR not less than 4 weeks after the initial response. The same methodology (CT or MRI) and scan acquisition techniques (including use or nonuse of IV contrast) as was used for the screening assessments should be utilized across all time points to allow consistent comparison of lesions. After treatment discontinuation for a reason other than PD, tumor assessments should continue to be performed as per the tumor assessment schedule until documentation of progression or start of a new anticancer agent. Screening CT scans should be performed with oral and iodinated intravenous contrast and MRI scans should be performed with intravenous gadolinium chelate. Post-screening scans may be performed without contrast if a medical contraindication develops while on study treatment. If iodinated intravenous contrast is contraindicated, chest CT should be done without intravenous contrast. MRI should be performed for all other body regions (with gadolinium unless contraindicated (eg, severe renal dysfunction).

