**Table 5 Schedule of Assessments in Study E7080-G000-230 – Randomization Phase**

Phase	Prerandomization		Randomization a (All cycles are 21 days in duration)																		
	Screening b	Baseline c	Treatment d															Off-Tx	Follow-up e		
Period	1	2	3	4	5	6	7	8	9	10	11	12	13	14	15	16	17	18+			
Visit	1	2	3	4	5	6	7	8	9	10	11	12	13	14	15	16	17	18+			
Cycle			Cycle 1			Cycle 2			Cycle 3			Cycle 4			Cycle 5			Cycle 6-X			
Day	-28 to -2	-1	1	8	15	1	8	15	1	8	15	1	8	15	1	8	15	1			
Procedures/Assessments																					
Palatability Questionnaire g			X																		
Tumor assessments: CT/MRI f	X		CT chest and CT/MRI of other areas of known disease at Screening plus any areas of newly suspected disease should be performed every 6±1 week or sooner if clinically indicated until Week 18±1 week, then every 9±1 weeks until Week 54±1 week. Thereafter, to be performed every 12±2 weeks until documentation of PD.															X			
Brain CT/MRI f	X		Brain scans will be performed at screening as clinically indicated, and thereafter during treatment if clinically indicated. For subjects with protocol-eligible, treated brain metastases at Screening, brain scans should be performed at all tumor assessment time points.																		
Height t		X	X												X				X	X	X
Tanner Stage u		X																	X	X	X
Proximal Tibial growth plates x-ray t		X																X			
HRQoL		X	HRQoL will be collected on C2D1, C3D1, Week 18, C8D1, and C18D1															X			
Pharmacodynamic biomarkers v		X		X	X										X				X		
Archival tumor block or slides w			X																		
Survival x						X															X
Concomitant medications y			Throughout															X			
AEs/SAEs z			Throughout															X			

AE = adverse event, BP = blood pressure, C1D1 = Cycle 1 Day 1, C1D2 = Cycle 1 Day 2, C1D8 = Cycle 1/Day 8, C1D15 = Cycle 1 Day 15, CR = complete response, CT = computerized tomography, h = hour, HR = heart rate, HRQoL = Health-Related Quality of Life, IV = intravenous, IVRS = Interactive Voice Response System, MRI = magnetic resonance imaging, PD = progressive disease/disease progression, PK = pharmacokinetics, PR = partial response, PS =

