**Table 5 Schedule of Assessments in Study E7080-G000-230 – Randomization Phase**

Phase	Prerandomization		Randomization a (All cycles are 21 days in duration)																	
	Screening b	Baseline c	Treatment d																Off-Tx	Follow-up e
Period	1	2	3	4	5	6	7	8	9	10	11	12	13	14	15	16	17	18+		
Visit	1	2	3	4	5	6	7	8	9	10	11	12	13	14	15	16	17	18+		
Cycle			Cycle 1			Cycle 2			Cycle 3			Cycle 4			Cycle 5			Cycle 6-X		
Day	-28 to -2	-1	1	8	15	1	8	15	1	8	15	1	8	15	1	8	15	1		
Procedures/Assessments																				

**Treatment Phase:** Tumor assessments of the chest, and other areas of known disease at Screening or newly suspected disease should be performed every  $6\pm 1$  weeks from C1D1 until Week  $18\pm 1$  week, then every  $9\pm 1$  weeks until Week  $54\pm 1$  week, and thereafter, every  $12\pm 2$  weeks until documentation of PD during the Treatment Phase (or sooner if there is evidence of progressive disease) and should utilize the same methodology (CT or MRI) and scan acquisition techniques (including use or nonuse of IV contrast) as was used for the screening assessments. Tumor response will be assessed according to RECIST 1.1. Subjects who discontinue must complete the off-treatment tumor assessment. Any CR or PR must be confirmed not less than 4 weeks following the initial achievement of the response. After treatment discontinuation, tumor assessment should continue to be performed according to the schedule: every  $6\pm 1$  weeks until Week  $18\pm 1$  week, then every  $9\pm 1$  weeks until Week  $54\pm 1$  week, thereafter, to be performed every  $12\pm 2$  weeks until documentation of progression or start of a new anticancer agent.

- s. Brain CT with contrast or MRI pre- and post- gadolinium contrast will be performed at the Screening Visit as clinically indicated, and thereafter during treatment as clinically indicated. For subjects with protocol-eligible treated brain metastases, brain CT/MRI will be performed at all tumor assessment time points.

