#### 8.7.1.1.2 SECONDARY ENDPOINTS

- Progression-free survival rate at 1 year (PFS-1y rate) by IIR is defined as the percentage of subjects who are alive and without PD at 1 year from the randomization date as determined by IIR of radiological imaging using RECIST 1.1. The PFS-1y rate is estimated on the full analysis set for this study using the K-M method.
- Progression-free survival (PFS) by IIR is defined as the time from the date of randomization to the date of the first documentation of PD or death (whichever occurs first) as determined by IIR using RECIST 1.1.
- Overall survival (OS) is defined as the time from the date of randomization to the date of death from any cause. Subjects who are lost to follow-up and those who are alive at the date of data cutoff will be censored at the date the subject was last known alive, or date of data cutoff, whichever occurs first. Overall survival rate at 1 year will be estimated.
- Objective response rate (ORR) by IIR at 4 months is defined as the proportion of subjects who have best overall response of complete response (CR) or partial response (PR) as determined by IIR using RECIST 1.1 within the first 4 months.
- Safety will be assessed summarising the incidence of TEAEs and SAEs together with all other safety parameters.
- Assessment of population-based PK parameters of lenvatinib.
- Score changes from baseline for all PedsQL scales including Generic Core Scales and Cancer Module. Scores will be calculated for total generic score, total cancer score, each physical function subscale including physical health, psychosocial health, emotional function, social function, school/work function in the Generic Core Scales, and each subscales in the cancer module.
- Palatability and acceptability of the suspension formulation of lenvatinib in subjects receiving the suspension formulation in the study will be assessed using the Palatability Questionnaire (see [Appendix 5](#)).

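### The 4-month ORR window closes a few days before the nominal Week 18 scan, so whether a response first seen at that scan counts depends on the exact scan day

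*Protocol*

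**What the plan says.** Protocol Section 8.7.1.1.2 and the synopsis (Secondary Endpoints) define ORR by IIR at 4 months as the proportion of subjects with "best overall response of complete response (CR) or partial response (PR) as determined by IIR using RECIST 1.1 within the first 4 months".

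The scan calendar is in Section 8.5.1.2.1 and Table 5. Scans run "following the start of treatment on Cycle 1 Day 1 during the chemotherapy treatment period until Week 18"; Table 5 says they "should be performed every 6±1 week or sooner if clinically indicated until Week 18±1 week, then every 9±1 weeks until Week 54±1 week". Scheduled assessments are therefore Weeks 6, 12, 18 and 27, and so on. Extra scans are possible: "At any point, scans should be performed earlier than the scheduled time point, if clinically indicated".

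On confirmation, Section 8.5.1.2.1 says that an initial CR or PR "must be confirmed by IIR not less than 4 weeks after the initial response", and the tumor-assessment footnote to Table 5 says "Any CR or PR must be confirmed not less than 4 weeks following the initial achievement of the response". Both set a minimum gap. Neither sets a latest date or says whether the confirming scan must itself lie within the 4 months.

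Elsewhere the protocol works with Week 18. The binomial sensitivity analysis of PFS-4m cuts at 18 weeks (Section 8.7.1.6.1), and removal of existing lesions is permitted only after the Week 18 tumor assessment (Sections 8.2 and 8.4.7.3).

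**The concern.** The endpoint window and the scan calendar do not meet. The chemotherapy lasts up to 5 cycles of 21 days (15 weeks), so Week 18 is the first scheduled scan after it ends. The ORR window closes about 4 days before that scan is due. Two subjects whose response is first seen at the Week 18 visit, both scanned within the permitted tolerance, can be classified differently because one came in on Day 121 and the other on Day 124.

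The confirmation rule adds a second uncertainty. A response first seen at Week 12 is normally confirmed at Week 18. Whether that subject is a responder can depend on a choice the endpoint wording does not make.

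At stake is the meaning and reproducibility of a secondary endpoint that Section 8.7.1.6.2 compares formally between arms. With 36 subjects per arm, each reclassified subject moves an arm's ORR by 1/36 = 2.8 percentage points.

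**Working it through.** The protocol gives no target ORR, power or responder count for this endpoint, so there is no design figure to reproduce. The check is a calendar calculation.

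**Inputs**
- Window: 4 months = 4 × 30.4375 = 121.75 days = 17.39 weeks. Depending on the month convention it is 120 to 123 days.
- Scan days after Cycle 1 Day 1, ±7 days (Section 8.5.1.2.1, Table 5): Week 6 = 35–49, Week 12 = 77–91, Week 18 = 119–133, Week 27 = 182–196.
- Confirmation: at least 28 days after the initial response.
- Assumption: the ORR clock starts at randomization, on the same day as Cycle 1 Day 1, where Table 5 places it. An earlier randomization would close the window sooner relative to the scans.

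**Step 1: share of the Week 18 window that lies inside 4 months**

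| 4 months read as | Days inside, of 15 | Share |
|---|---|---|
| 120 days | 2 | 13% |
| 121.75 days | 3 (119–121) | 20% |
| 122 days | 4 | 27% |
| 123 days | 5 | 33% |
| 18 weeks = 126 days | 8 | 53% |

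The nominal date, Day 126, is 126 − 121.75 = 4.25 days late. The 20% assumes scan days spread evenly over the window; clustering around the nominal date would lower it.

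**Step 2: a response counts from first documentation, with confirmation at any later time**
- First seen at Week 6 or 12: latest day 91, always inside.
- First seen at Week 18: inside on 3 of 15 days, so 80% of window days exclude it.

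**Step 3: the confirming scan must also fall within 4 months**
- First seen at Week 6: confirmed at Week 12, by Day 91 at the latest; always inside.
- First seen at Week 12: the next scheduled scan is Week 18. The smallest gap, Week 13 to Week 17, is exactly 28 days, so that scan can always confirm. It falls inside the window on only 3 of 15 days, so about 80% are lost.
- First seen at Week 18: confirmed on Days 182–196, never inside.
- An unscheduled scan 28 days after a Week 12 scan (Days 105–119) would be in time, but it is not required.

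**Step 4: illustration only**

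The protocol does not give the timing of first response, so the splits over Weeks 6/12/18 are assumed. Share counted in Step 2 = w6 + w12 + 0.2 × w18. Share counted in Step 3 = w6 + 0.2 × w12.

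| Assumed split (%) | Step 2 | Step 3 |
|---|---|---|
| 60/30/10 | 92% | 66% |
| 50/35/15 | 88% | 57% |
| 40/40/20 | 84% | 48% |
| 20/50/30 | 76% | 30% |

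The shares are of subjects whose response is first seen by Week 18 and can be confirmed.

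**The case against.** The best defense is that nothing in the protocol requires the confirming scan to fall inside the 4 months. The exploratory definition of duration of response (Section 8.7.1.1.3) starts the clock when a response is first documented, and the Table 5 footnote treats confirmation as something that follows the initial achievement of response. Read that way, every Week 12 responder counts. The confirmation detail could also be settled in the SAP, which is not shown.

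This stands. A reader might infer that the written rule counts only Week 6 responders, or simply miscounts responders. The documents do not support that: it follows only on the stricter reading, and even then some Week 12 responders count through an early Week 18 scan or an unscheduled one. On confirmation, the fair finding is an ambiguity.

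The defense does not reach the Week 18 scan. The 4-month limit and the scan calendar are both fixed in the protocol, and on the lenient reading the window still closes before the nominal scan date.

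It is also fair to say that ORR is an unpowered secondary endpoint, and that Section 8.2 itself notes that bone lesions in this disease do not shrink, so few responses may occur under any rule.

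**Conclusion.** The point holds as a mismatch between the endpoint window and the scan schedule. With 4 months taken as 121.75 days and scan days spread evenly, about 20% of the Week 18 window (13% to 33% across month conventions) lies inside, so most responses first seen at that scan are excluded on the accident of the scan date. If confirmation must also fall within 4 months, about 80% of Week 12 responders are lost too; the text leaves that open.

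A reader might go on to infer that the difference between arms shrinks. The documents do not support this: both arms share the schedule, and no arm-specific response timing is given. Nor can responder counts be predicted. The 12.5% ORR cited from Study 207 in Section 6.3.1 is a rate as of a data cutoff rather than a 4-month rate, and the timing splits above are assumptions. The primary PFS-4m analysis does not use the ORR definition and is unaffected. The change is worth making because it removes an arbitrary rule at almost no cost.

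**What to change.** In Section 8.7.1.1.2 and the synopsis, define the endpoint as ORR by IIR through the Week 18 (±1 week) tumor assessment. A responder is a subject whose CR or PR is first documented at or before that assessment and is confirmed by IIR at least 4 weeks later at any subsequent assessment, including one after 4 months. This agrees with the 18-week cut already used in the PFS-4m sensitivity analysis and settles the confirmation question.

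One consequence needs a rule. Lesions may be removed after the Week 18 assessment, and the next scheduled scan is Week 27, so some Week 18 responders may have no evaluable confirming scan. Report those whose lesions are removed before confirmation separately, with a sensitivity analysis that counts them as responders.

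The cost is one sentence in each place and one extra table row, with no added scans or subjects. The small downside is that some Week 18 responses wait for the Week 27 scan (Day 196 at the latest). For subjects still being followed, that precedes a cutoff set by 18 completed cycles (18 × 21 = 378 days). Because the cutoff can come sooner if the last subject discontinues early, the SAP should check that late-enrolled subjects' Week 27 scans are captured.
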